 - At least 5 episodes with vestibular symptoms of moderate or severe intensity, lasting 5 min to 72 hours
 - Only one of the criteria B and C for vestibular migraine is fulfilled (migraine history or migraine features during the episode)
 - Not better accounted for by another vestibular or ICHD diagnosis

3. Written informed consent obtained from subject and ability for subject to comply with the requirements of the study.
4. Baseline (SV1) and SV2 VM-PATHI score > 25
5. Baseline (month 0 to 1) definitive dizzy days > 4
6. Fluency in English
7. 80% adherence or better to daily text message during baseline phase
8. Written informed consent
9. Access to email, and cell phone

a. Exclusion Criteria

1. Pregnant, breastfeeding, or unwilling to use approved form of birth control during participation in the study.
2. Presence of a condition or abnormality that in the opinion of the Investigator would compromise the safety of the patient or the quality of the data.
3. Allergy to galcanezumab
4. Prior treatment with galcanezumab
5. History of ear surgery (other than ear tubes)
6. Other vestibular diagnosis (excluding treated BPPV- Benign Paroxysmal Positional Vertigo). This includes Meniere's disease, superior canal dehiscence syndrome, vestibular neuritis,

persistent postural perceptual dizziness, unilateral or bilateral vestibular loss, cerebellar or brainstem disease, multiple sclerosis, Mal de Debarquement, Third window syndrome, vestibular paroxysmia, vestibular schwannoma, psychiatric dizziness, central dizziness, multifactorial dizziness, dizziness due to cerebrovascular disease, post-concussive dizziness, and cervicogenic dizziness.

7. Failure of treatment with > 4 prophylactic migraine medications
8. Prior or current treatment with a CGRP medication
9. Pregnant/breastfeeding if female
10. History of serious medical or psychiatric disease, at the discretion of the treating physician (including significant coronary artery disease, peripheral vascular disease, cerebrovascular disease, kidney disease, liver disease, Raynaud's disease, uncontrolled psychiatric disease or past psychiatric hospitalization)
11. History of mania, psychosis, or suicidal ideations
12. Ok if on up to 2 migraine prophylactic medications (prescribed for that purpose), dose must be stable for 2 months prior to study start.

Rationale:

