These inclusion/exclusion criteria were chosen so that the study has as much real world applicability as possible, while also minimizing risks to subjects. Based on our preliminary data, we believe that with these inclusion and exclusion criteria, and accounting for subjects who don't want to participate and also dropout, we will still be able to recruit enough subjects to meet our recruitment goals within 2 years.

Sample Size:

We have specifically designed this as a pilot study due to lack of data to help inform sample size calculations. However, hypothesizing a difference between VM-PATHI scores between groups of 7 points, and using the standard deviation from the validation of the instrument, we with 50 subjects total, or 25 per arm, we will have 90% power to detect a significant difference at the 0.05 level between groups to assess the efficacy of galcanezumab for vestibular migraine. If we assume a 10% dropout rate in the trial we will still have greater than 80% power to detect a difference.

Clinical Sites:

We will perform this study as a single center. We will be recruiting subjects from both the Otolaryngology-Head and Neck Surgery and Neurology departments. In a previous study where we developed the VM-PATHI, we were able to recruit around 80 subjects with vestibular migraine in a little over 1 year.

Study Visit Timeline:

The study visits will be scheduled within +/- 4 days of the expected timeline. This flexibility is based on the clinic availability dates of the PI and other providers.

- Study Visit 1 (SV1) = Day 0 / Month 0
- Study Visit 2 (SV2) = Day 30 / Month 1
- Study Visit 3 (SV3) = Day 60 / Month 2
- Study Visit 4 (SV4) = Day 120 / Month 4

Re-Enrollment Policy:

For participants who met all inclusion criteria AND none of the exclusion criteria (except for not having the minimum required VM-PATHI score and/or definitive dizzy days), they can re-enroll in the study at a later date when they feel their symptoms are worse. At that time, the participant would have to start over from Day 0 and undergo screening again.

Randomization:

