- Randomization will be done based on meeting final study criteria at SV2. So, if two patients are seen on the same day for SV1 and SV2, it would be the order of patients being seen at SV2. This would only come into play if the patients are part of the same randomization schedule (i.e. same sex and diagnosis). If however, two or more patients in the same randomization strata are seen for SV2 on the same day, given that the prescription is picked up in the AM, if the first patient does NOT meet study criteria, then we will keep the order of randomization (because the drugs are prelabelled for each patient)- but subsequent to that the next subject in that strata who is randomized should take the place of the subject who didn't meet criteria, so as to avoid disruptions to the randomization strategy.

- Packaging and labeling of test and control treatments will be identical to maintain the blind.
- Each subject will be given an identical study packet, containing their assigned drug, along with study information.
- The study blind will be broken on completion of the clinical study and after the study database has been locked. Investigators will be made aware of their subjects' treatment designations only after all the data has been collected and analyzed.
- During the study, the blind may be broken only in emergencies when knowledge of the patient's treatment group is necessary for further patient management. When possible, the Investigator should discuss the emergency with the Medical Monitor prior to unblinding. If it is determined that it is medically necessary to break the blind, the medical monitor will inform the investigator about the study status of that subject. That will be considered a protocol violation, and that subject will be removed from the study.

Intervention:

The study drug will be administered with a subcutaneous injection of galcanezumab or placebo. The first dose (at month 1) will be a loading dose of two injections, or 240 mg in total. After that, at month 2, and month 3, each subject will get either a subcutaneous injection of galcanezumab 120 mg or placebo. The injections will be with a pre-loaded syringe containing either galcanezumab or placebo.

Quality Assurance:

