The active drug and placebo will be managed through the research pharmacy at UCSF. The drug and placebo will be supplied by Eli Lilly and Company. Study drugs will be given to patients on the day of randomization (month 1), so any failure of subjects to take the study drugs will just be considered a violation of protocol, but they will be included in the intent to treat analysis.

Packaging:

Study drug will be supplied in preloaded syringes, each with a dose of 120 mg or placebo. Subjects will first receive the first month's supply (240 mg or placebo) at study visit 2, and then will receive a two-month supply at study visit 3. So, at study visit 2 and 3, each participant will get two pre-filled syringes. They will also get an insulated bag with a cold pack to keep the drug cool until it can be refrigerated at home.

Labeling:

Each carton (kit) of study drug will be labeled with the required FDA warning statement, the protocol number, a treatment number, the name of the sponsors, and directions for patient use and storage.

Dosage:

The study drug will be administered in fixed dose of 120 mg. The first administration, at month 1, will be a loading dose of 240 mg. Each subsequent injection (month 2 and 3) will be 120 mg dose. There will be no dose adjustment for weight, age, or any other factors

Dispensing of Study Drug:

Drugs will be administered in a packet with a 1-month supply by the site investigator at study visit 2. They will then get the second 2-month supply at study visit 3.

Administration of Study Drug:

Subjects will self-administer the drug, with a pre-filled syringe, into an acceptable area of the body. This is typically the thigh, but also includes the abdomen, buttocks, or back of the upper arm. Study personnel will monitor with first and second injection to ensure compliance and proper administration. A note will be placed into the medical record confirming the time, date, and location of the injection (part of the body). For the third injection, the CRC will reach out to the patient to confirm injection, and then record time, date, and anatomic site of the injection. Adherence to the injection will be confirmed by asking participants to send the CRC a picture of the empty syringe. This picture will be uploaded to the REDCap record.

Storage of Study Drug:

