The protocol and consent form will be reviewed and approved by the UCSF IRB prior to study initiation. Serious adverse experiences regardless of causality will be reported to the IRB in accordance with the standard operating procedures and policies of the IRB, and the Investigator will keep the IRB informed as to the progress of the study. The Investigator will obtain assurance of IRB compliance with regulations.

Data Analysis Plan:

Subjects will be divided by study status into several groups.

1. Per Protocol Analysis
 - a. Signed Consent
 - b. 4 study visits (in person or virtual) within:
 - i. SV2 (day 30) no earlier than day 23, and no later than day 44.
 - ii. SV3 (day 60/day 30 after SV2) no earlier than day 23 after SV2, and no later than day 37 after SV2.
 - iii. SV4 (day 120/day 60 after SV3) no earlier than day 50 after SV3, and no later than day 70 after SV3.
 - c. Received same drug (galcanezumab or placebo) for all doses during the trial
 - d. Completed Day 90 injection within 7 days of target date, so 23 to 37 days after SV3
 - e. 80% or better adherence to text message
 - f. Filled out all questionnaires
2. Intent to Treat
 - a. Everyone who signed consent and got at least one dose of study drug who does not meet per protocol criteria
3. SV2 failure
 - a. Signed consent but did not meet eligibility during the baseline month (less than 80% adherence to texting, or fewer than 4 definitive dizzy days or SV2 VM-PATHI less than 25)
4. SV1 failure
 - a. Signed consent but then VM-PATHI score too low on SV1
5. Screen failure
 - a. Did not meet inclusion/Exclusion so did not sign consent

Responsibilities of Study Team Members:

[name] (Principal Investigator): [name] is an Assistant Professor in the Department of Otolaryngology – Head and Neck Surgery, and the director of the Balance and Falls Center at UCSF. [name] will serve as PI for this project, and will supervise experimental design, data analysis, and summarizing the result for public disclosures to the academic community.

[name]: Co-investigator: [name] is an Assistant Professor of Neurology, and a member of the UCSF Headache Center. She will assist will all aspects of the study.

[name]: [name] is the director of the Headache Center at UCSF, and will assist in all aspects of the study.

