Appendix 1: Schedule of study events

Study month	0	1	2	3	4
Clinical Visit	✓ (L5) SV 1	✓ (L4) SV 2	✓ (L4) SV 3		✓ (L4) SV 4
Phase of study	Baseline Eval	Randomize/Start Treatment	First eval on Tx		Final eval for data/safety
Testing	CBC	✓			✓
	CMP	✓			✓
	EKG	✓			✓
	Pregnancy Test	✓			
	Audio (if not previously done)	✓			
	Vital signs	✓	✓	✓	✓
Questionnaires	VM-PATHI	✓	✓	✓	✓
	DHI		✓	✓	✓
	HIT-6		✓	✓	✓
	PROMIS SF v1.2- Global Health		✓		✓
	Med review	✓	✓	✓	✓
	Adverse Effects			✓	✓
	Medical history	✓			
	Demographics	✓			
	PHQ-9		✓		✓
	GAD-7		✓		✓

	Diagnosis form	√				
	Close-out form					√
Definitive Dizzy Day Text		√	√	√	√	√
Treatment			240 mg Emgality/Placebo	120 mg	12 0 mg	

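### In the available text the only scheduled pregnancy test is best read as at SV1, nominally 30 days before randomisation and the loading dose, so the pregnancy exclusion is not confirmed by test at first dosing

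*Combined protocol and SAP*

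**What the plan says.** Exclusion Criteria, item 1, rules out subjects who are "Pregnant, breastfeeding, or unwilling to use approved form of birth control during participation in the study". The shorter list under Subject Selection has the same exclusions.

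Eligibility is settled at the second visit. The Blinding section states: "Randomization will be done based on meeting final study criteria at SV2". Appendix 1 labels the month 1 phase "Randomize/Start Treatment". Pharmacy/Study Drug puts supply at the same point: "Study drugs will be given to patients on the day of randomization (month 1"). Under Intervention, the first dose, at month 1, is the 240 mg loading dose or placebo.

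Data Collection names Appendix 1 as the schedule for the data points. Its row "Pregnancy Test" carries one tick. On visit timing, Study Visit Timeline puts SV1 at day 0 and SV2 at day 30, and adds: "The study visits will be scheduled within +/- 4 days of the expected timeline".

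Early Discontinuation of Study Drug lists a positive pregnancy test among the possible reasons for stopping treatment.

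**The concern.** The protocol already accepts that eligibility can change between SV1 and SV2. It measures VM-PATHI again at SV2 and judges dizzy days and text-message adherence over the intervening month. Pregnancy status can change in that month too, but no test is scheduled at its end.

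A subject who conceives around SV1, or during the baseline month, could therefore receive the loading dose while meeting an exclusion criterion, with a negative SV1 result on file. What is at stake is an avoidable exposure of the kind the sponsor's own exclusion is meant to prevent. The documents give no pregnancy rate and no reproductive-risk data for the drug, so no size can be put on that risk.

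**Working it through.** No power, alpha or event figure is involved. The check is a reading of Appendix 1 followed by date arithmetic.

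**Step 1: which column holds the tick.** The table was flattened in extraction, so the row is compared with its neighbours.

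| Row in Appendix 1 | Blanks before first tick | Ticks | Reading |
|---|---|---|---|
| VM-PATHI | 0 | 4 | SV1, SV2, SV3, SV4 |
| DHI | 1 | 3 | starts at SV2 |
| Adverse Effects | 2 | 2 | starts at SV3 |
| CBC, CMP, EKG | 0 | 2 | SV1 and SV4 |
| Medical history, Demographics | 0 | 1 | SV1 |
| Pregnancy Test | 0 | 1 | SV1 |

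The columns follow the four visits, and the pregnancy test sits in the first. Unlike the blood tests and EKG, it is not repeated.

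**Step 2: other sections.** No available section schedules a pregnancy test at SV2 or later. Scheduled tests at or after SV2: 0.

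**Step 3: age of the result at first dosing** (SV2 day minus SV1 day, with SV1 = day 0).

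- Nominal: 30 − 0 = 30 days.
- Study Visit Timeline, 4 days either way: 30 − 4 = 26 to 30 + 4 = 34 days.
- Data Analysis Plan, per-protocol window for SV2 of day 23 to day 44: 23 to 44 days.
- With a test at SV2 before drug is handed over: 0 days.

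The two ranges answer different questions. The first is how visits are to be scheduled. The second is how far SV2 may drift before the subject leaves the per-protocol set.

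**The case against.** The best case for the plan as written has four parts.

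- **Birth control is required throughout participation**, which covers the interval between SV1 and SV2. This stands as a real reduction in risk. It does not verify status, and the sponsor's own SV1 test shows that it does not rely on contraception alone.
- **Final criteria at SV2 can be read to include not being pregnant.** That is a fair reading: the exclusion does not lapse, and staff could ask. What is missing is a stated method; no available section requires a test or a history at that visit.
- **A positive test is a listed reason to stop treatment**, so the plan envisages testing after SV1, at least when indicated. True, but treatment begins at SV2, so this acts only after exposure, and no routine test is scheduled to trigger it.
- **The instruction may be in text that was not available.** Data Collection refers to instructions in Appendix 2, of which only the heading could be read, and a portion just before Appendix 1 was removed. This cannot be excluded, and it limits confidence to medium. Appendix 1, as the named schedule, would still need the tick.

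A reader might also infer support from the Data Analysis Plan, where the SV2-failure group names only "less than 80% adherence to texting, or fewer than 4 definitive dizzy days or SV2 VM-PATHI less than 25". On that reading, a subject found pregnant at SV2 would have no status group at all, since the intent-to-treat group is "Everyone who signed consent and got at least one dose of study drug who does not meet per protocol criteria" and she has had no dose. The documents do not support this inference. The SV1-failure group also omits pregnancy, although a test is scheduled at SV1, so silence in these labels says nothing about when tests are done. The reasons in brackets may also be only examples, in which case the general SV2-failure wording would cover her.

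**Conclusion.** The point holds as a low-cost safety improvement. On the available text, the pregnancy exclusion is checked by test once, nominally 30 days before the loading dose (26 to 34 days as scheduled; 23 to 44 days within per-protocol limits), and is not confirmed by test when drug is first given.

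This rests on reading the single tick as SV1, which the neighbouring rows support, and on there being no contrary instruction in the unavailable text.

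Two stronger conclusions might be drawn, and neither is supported. The plan does not permit dosing a subject known to be pregnant; the gap is in verification. Nor is there any consequence for power, alpha or the efficacy analyses. The documents state no testing standard that the schedule breaches.

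**What to change.** **Preferred.**

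1. In Appendix 1, add a pregnancy-test tick at SV2 for female subjects who could be pregnant, done before study drug is handed over. Testing every female subject up to age 75 is not needed.
2. In the Blinding section, state that a positive SV2 result means the final study criteria are not met. The existing rule there on keeping allocation order when a same-day subject fails at SV2 can then apply unchanged.

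The cost is one simple test per eligible subject at an existing visit. If it is done after the other SV2 checks are passed, the ceiling is 50 tests plus any positives. That assumes all 50 planned subjects are female and could be pregnant; the sex split is not given.

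**Minimum.** Move the SV1 test to SV2, with the same sentence in the Blinding section. This adds no procedure. The downside is that a pregnant subject may complete the drug-free baseline month before being excluded.

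Adding a positive pregnancy test to the failure groups in the Data Analysis Plan is optional housekeeping. Either option addresses first dosing only; neither covers conception after SV2.

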Dizziness Handicap Inventory (DHI): This is the most widely used measure of dizziness severity, and consists of 25 questions. Questions ask about problems related to dizziness, and are scored as no (0 points), sometimes (2 points), or always (4 points). Total score is between 0 and 100, with higher scores indicating more disability. While subjects with vestibular migraine suffer from a variety of symptoms, dizziness is clearly the predominant feature. Furthermore, this will help us compare data to other studies that involve causes of dizziness.

PROMIS SF v1.2- Global Health: This is a widely used and validated quality of life measure. It is quick and simple to administer. There are 10 questions on this scale, each with a score of 1-5. Higher scores correspond to a greater extent of the concept measured (e.g., more fatigue, more pain). Two summed scores are generated, one for global mental health (question #3, 6, 7, 8) and one for global physical health (question #2, 4, 5, 10). The remaining 2 questions are analyzed separately. Summed scores for global physical health and global mental health are converted into T-score values using the "HealthMeasures Scoring Service" (https://www.assessmentcenter.net/ac_scoringservice). The T-scores for physical health and mental health can then be grouped into excellent, very good, good, fair, and poor categories. The cut points for each category is determined by calculating the midpoint between 2 adjacent means. For example, if the mean mental health T-score for “Excellent” is 61 and the mean mental health T-score for “Very Good” is 51, then the cut point for these categories would be a T-score of 56.

Data Collection:

Data collection will be performed by the clinical research coordinator during each study visit. This data will be entered into the REDCap database by the research coordinator. VM-PATHI, DHI, GAD-7, PHQ-9, PROMIS SF v1.2- Global Health, and HIT-6 will be administered electronically via REDCap to the subject during the study visit. The schedule of collection of each data point is reviewed in appendix 1. The data collection instructions are contained within appendix 2.

Stopping Rules:

There will be no stopping rules for this trial, given the short duration of the study. Each adverse effect and serious adverse effect will be reviewed by the data safety monitoring team, and subjects may be unblinded and/or the study will be stopped early for serious safety concerns.

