- Early Discontinuation of Study Drug:**

- o A subject may be discontinued from study treatment at any time if the subject, the investigator, or the Sponsor feels that it is not in the subject’s best interest

to continue. The following is a list of possible reasons for study treatment discontinuation:

- Subject withdrawal of consent (or assent)
- Subject is not compliant with study procedures
- Adverse event that in the opinion of the investigator would be in the best interest of the subject to discontinue study treatment
- Protocol violation requiring discontinuation of study treatment
- Lost to follow-up
- Sponsor request for early termination of study
- Positive pregnancy test (females)

If a subject is withdrawn from treatment due to an adverse event, the subject will be followed and treated by the Investigator until the abnormal parameter or symptom has resolved or stabilized. All subjects who discontinue study treatment should come in for an early discontinuation visit as soon as possible and then should be encouraged to complete all remaining scheduled visits and procedures. All subjects are free to withdraw from participation at any time, for any reason, specified or unspecified, and without prejudice. Reasonable attempts will be made by the investigator to provide a reason for subject withdrawals. The reason for the subject's withdrawal from the study will be specified in the subject's source documents.

c. Analysis of Primary Endpoint:

d. For the primary endpoint, which is the change in VM-PATHI scores between month 1 and month 4 as compared between the galcanezumab arm and the placebo arm, a paired two-tailed Student's t-test will be used, provided the data is normally distributed. This will be conducted with an intent-to-treat analysis. Significance will be set at alpha of 0.05.

e. Analysis of Secondary Endpoints:

Definitive dizzy days/month, comparing baseline (month 0 to 1) to after treatment (month 3-4), between active treatment and control arms, will be assessed using a two-tailed t-test.

Response rates will be reported per category (100%, 75%, 50%, 25%, and 0% reduction in definitive dizziness days, comparing month 0 to 1 to month 3 to 4) for both active treatment and control arms. Number of subjects who experience 50% of better reduction in dizziness days will be compared using Chi Squared test.

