Dizziness Handicap Inventory will be compared between active treatment and control arms, looking at change in score from baseline to month 4, using a two-tailed t test.

PROMIS scores comparing active and placebo arm score changes from before (month 0) and after (month 4) treatment using a paired t-test.

Safety and tolerability data will be summarized by treatment group.

Adverse event rates will be coded by body system and MedDra classification term. Adverse events will be tabulated by treatment group and will include the number of patients for whom the event occurred, the rate of occurrence, and the severity and relationship to study drug.

Initially data will be summarized overall, by patient, and by treatment and control groups. Plots of each outcomes will be displayed graphically over longitudinal time points. Univariate summaries of all variables overall, by patient, and by subgroup will include means and standard deviations for continuous variables and counts and percentages for categorical variables.

Bias:

Bias will be minimized by using a double-blinded study design, with allocation concealment. This will limit selection, performance, and detection bias. In addition, this will help control for potential confounding variables. In addition, by including a placebo control group, we will minimize regression to the mean bias. Finally, by collecting information prospectively, we will minimize reporting bias.

Missing Data:

We will minimize missing data by having the clinical trial coordinator present to help the study subject fill out all data. We anticipate a 15-20% loss to follow up, and have accounted for that in our sample size calculations. Outliers and non-compliant subjects will be included in the analysis. We will perform an intent-to-treat analysis.

Trial Duration:

We estimate that this trial will take approximately 2 years to complete, once subject recruitment is able to begin. That includes 1.5 years for subject recruitment and data collection, and 6 months for closeout and data analysis. If recruitment is slower than expected, we will plan on keeping the trial open for a longer period of time. This seems unlikely based on our prior experience with recruitment in this patient population.

Pharmacy/Study Drug:

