The Investigator will probe, via discussion with the subject, for the occurrence of AEs during each subject visit and record the information in the site's source documents. Adverse events will be recorded in the patient CRF. Adverse events will be described by duration (start and stop dates and times), severity, outcome, treatment and relation to study drug, or if unrelated, the cause.

g. Serious Adverse Experiences (SAE):

SAE is defined as any AE occurring at any dose that results in any of the following outcomes:

- Death

- A life-threatening adverse experience
- inpatient hospitalization or prolongation of existing hospitalization
- A persistent or significant disability/incapacity
- A congenital anomaly/birth defect
- Other important medical events may also be considered an SAE when, based on appropriate medical judgment, they jeopardize the subject or require intervention to prevent one of the outcomes listed

Serious Adverse Experience Reporting:

Study sites will document all SAEs that occur (whether or not related to study drug) per UCSF CHR Guidelines. The collection period for all SAEs will begin after informed consent is obtained and end after procedures for the final study visit have been completed. In accordance with the standard operating procedures and policies of the local Institutional Review Board (IRB), the site investigator will report SAEs to the IRB.

Privacy Protection:

The study will be conducted according to the Declaration of Helsinki, Protection of Human Volunteers (21 CFR 50), Institutional Review Boards (21 CFR 56), and Obligations of Clinical Investigators (21 CFR 312).

Clinical information will not be released without written permission of the subject, except as necessary for monitoring by the FDA. The Investigator must also comply with all applicable privacy regulations (e.g., Health Insurance Portability and Accountability Act of 1996, EU Data Protection Directive 95/46/EC).

Protocol Amendments:

Any amendment to the protocol will be written by the PI. Protocol amendments cannot be implemented without prior written IRB approval except as necessary to eliminate immediate safety hazards to patients. A protocol amendment intended to eliminate an apparent immediate hazard to patients may be implemented immediately, provided the IRBs are notified within five working days.

IRB:

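### Removing a subject from the study after emergency unblinding conflicts with the protocol's own follow-up and intent-to-treat rules, and may lose the month-4 outcome

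*Combined protocol and SAP*

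**What the plan says.** The Blinding list in the Randomization section limits code-breaking to real need: "the blind may be broken only in emergencies when knowledge of the patient's treatment group is necessary for further patient management". It then fixes the consequence: "That will be considered a protocol violation, and that subject will be removed from the study".

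Other sections bear on the same subject:

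- **Early Discontinuation of Study Drug** lists, among the reasons for stopping treatment, "Protocol violation requiring discontinuation of study treatment". For withdrawal from treatment because of an adverse event, it says "the subject will be followed and treated by the Investigator until the abnormal parameter or symptom has resolved or stabilized". Everyone who stops treatment is asked to attend a discontinuation visit and "then should be encouraged to complete all remaining scheduled visits and procedures".
- **Missing Data** states "Outliers and non-compliant subjects will be included in the analysis" and commits to intent-to-treat. **Analysis of Primary Endpoint** makes the same commitment.
- **Pharmacy/Study Drug** treats failure to take study drug as a protocol violation but keeps the subject in the intent-to-treat analysis.
- **Data Analysis Plan** defines its intent-to-treat group by consent, at least one dose, and not meeting the per-protocol criteria. Neither that group nor the per-protocol list mentions unblinding.
- **Serious Adverse Experience Reporting** has collection begin after consent and "end after procedures for the final study visit have been completed".
- **Stopping Rules** gives a second route to unblinding, after safety review: "subjects may be unblinded and/or the study will be stopped early for serious safety concerns". It says nothing about removal.

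**The concern.** The Blinding rule is mandatory, and it refers to the study rather than to study treatment. Elsewhere the protocol has separate language for stopping drug while staying in follow-up, and this rule does not use it. A coordinator who follows it as written would schedule no further visits.

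The trigger is a medical emergency after randomisation in which management turns on knowing the allocation. Such events can depend on treatment, so outcomes lost this way may be informatively missing. At stake are the subject's place in the primary comparison, the final safety evaluation, and any serious event between removal and month 4. The background section says that this pilot is meant to supply effect sizes for a larger trial, so a distorted arm mean would carry forward.

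**Working it through.** **1. The passages side by side.**

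- *Study drug.* The Blinding rule implies that it stops. Early Discontinuation covers stopping for a protocol violation. These are compatible.
- *Remaining visits.* The Blinding rule, read literally, ends them. Early Discontinuation encourages them. These conflict, and no text says which governs.
- *Serious adverse events.* Collection runs to the final visit. A removed subject has no final visit, so the end of collection is undefined.
- *Analysis set.* The Blinding rule is silent. Analysis of Primary Endpoint, Missing Data, Pharmacy/Study Drug and Data Analysis Plan all point to inclusion.

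**2. From removal to a lost outcome.** The primary analysis is a t-test on VM-PATHI change to month 4. In the Appendix 1 schedule, the month-4 score and the final data and safety evaluation both fall at the fourth visit. Removal before that visit leaves no month-4 score. Missing Data names no imputation or other method for absent scores. The subject therefore leaves the t-test even if nominally counted as intent-to-treat.

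**3. The plan's own figure.** The Sample Size section gives 25 per arm, a 7-point difference, alpha 0.05 and 90% power. The standard deviation is not given as a number, so the 90% cannot be reproduced independently. Solving for the SD that it implies (two-sided, two independent groups):

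- Normal approximation: SD = 7 / [(1.960 + 1.282) × √(2/25)] = 7.63.
- Exact noncentral t: SD = 7.48.

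**4. Effect on power, at SD 7.48 (exact t).** Power is 90.0% with 25 and 25, 89.4% with 24 and 25, and 88.7% with 23 and 25. The loss is 0.6 to 1.3 percentage points, which is minor.

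**5. Effect on the estimate.** Let k of 25 subjects in one arm be lost, and let their mean change be D points worse than the mean m of those retained.

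Full-arm mean = [(25 − k)m + k(m − D)] / 25 = m − kD/25, so the shift from losing them is kD/25.

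The documents give neither k nor D, so these values are assumed:

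- D = 10: shift 0.4 (k = 1) or 0.8 (k = 2).
- D = 20: shift 0.8 or 1.6.
- D = 30: shift 1.2 or 2.4. This is extreme, since 30/7.48 is about 4 implied SDs.
- D = 7 (no benefit for those lost, 7 points for the rest): shift 0.28 or 0.56. For k = 2 the mean benefit is 7 × 23/25 = 6.44 with both kept and 7.00 with both lost; 7/6.44 = 1.087, about 9% too high.

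The standard error of the arm difference at SD 7.48 is 7.48 × √(2/25) = 2.12, so the 0.56 shift is about 0.26 of a standard error. The shift favours the drug only if the subjects lost are in the active arm and do worse than the rest. Poorly responding placebo subjects lost in the same way would shift it in the opposite direction.

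**The case against.** The strongest reply is that the Blinding sentence should be read with the rest of the protocol. It calls unblinding a protocol violation, and Early Discontinuation lists a protocol violation as a reason to stop treatment, so the subject enters that pathway and is encouraged to complete the visits. The month-4 outcome is self-reported, so there is also a reason for caution about scores given once allocation is known. The number affected is likely to be very small.

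Part of this stands. The charitable reading is available, the caution about unblinded self-report is legitimate, and the numerical effect is modest. But the charitable reading has to override a specific, mandatory sentence with a general one that only encourages attendance. Nothing in the protocol tells a coordinator to do that.

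The reply also disposes of some stronger inferences that a reader might draw:

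- *That safety follow-up ends.* The documents do not say so. Follow-up until resolution or stabilisation probably covers the triggering event, although that sentence is written for withdrawal from treatment. Under the Data Safety Monitoring Plan the DSMB reviews serious events within 5 days.
- *That serious events vanish from the safety table, with 2/25 becoming 0/23.* The emergency precedes the unblinding and falls within the collection period. The adverse event tabulation excludes no one.
- *That the intent-to-treat principle is abandoned.* No passage excludes unblinded subjects' data. The risk comes through a month-4 score that is never collected.
- *That the rule would deter necessary unblinding.* This is speculation; the text expressly permits unblinding when medically necessary.

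**Conclusion.** The point holds as an unreconciled contradiction with a real, limited consequence. Followed as written, the Blinding rule can produce informative missing data: no month-4 VM-PATHI, no final safety evaluation, and no defined collection of later serious events. It is not a demonstrated loss of safety data or a demonstrated break in the intent-to-treat comparison.

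Each affected subject is 4% of an arm (1/25). Bias matters more here than power, and its size rests entirely on assumed counts and outcome differences. The conclusion depends on reading the removal literally and on the absence of any stated method for missing month-4 scores. The passages should be reconciled, but this alone does not undermine the trial.

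**What to change.** Amend the Blinding sentence so that it agrees with Early Discontinuation, Missing Data, Pharmacy/Study Drug, Data Analysis Plan and Serious Adverse Experience Reporting, and covers both unblinding routes. Suggested text:

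*Any unblinding of a subject during the trial is documented with its date and reason. Unless consent is withdrawn, the subject is asked to complete the remaining visits, questionnaires and AE/SAE collection, and stays in the intent-to-treat and safety summaries under the randomised arm.*

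Whether study drug continues is a separate decision, left to Early Discontinuation and not addressed here.

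If unblinded subjects are to be excluded from the per-protocol group, add that criterion to the Data Analysis Plan, whose list does not now mention unblinding. Add a sensitivity analysis of the primary endpoint omitting scores given after unblinding.

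The cost is a short amendment with IRB approval. The downside is that a few subjects may report VM-PATHI scores knowing their allocation; the sensitivity analysis shows how much that matters.
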